8.3 Analysis Visit Definition

Subjects who drop out after discontinuation of investigational product administration are required to perform a termination visit. If the termination visit date is included in the planned visit period and the corresponding visit result does not exist, the termination visit result is considered as the planned visit result and included in the

CONFIDENTIAL

analysis. If the result of the visit exists, the result closer to the planned visit in the protocol is considered as the result of the visit and is included in the analysis. If the absolute value of the difference between visits is the same based on the planned visit (e.g. -3 days, +3 days) previously measured results (day -3) are considered the results of the visit and included in the analysis. We also analyze the results of unscheduled visit in the same way. Listing presents the results of all visits, including unscheduled visits, regardless of whether or not the analysis visit is included.

The analysis visit is calculated as the measurement date, not the visit date.

Table 2 Analysis visit definition – 0-8 Vaccination schema

Analysis visit	Visit day Interval (days)	Visit window (days)	Analysis visit permitted window (days)
Visit 1 (Baseline)	0		
Visit 2	7	± 2	$5 \leq \text{Visit 2-Baseline} \leq 9$
Visit 3	56	± 3	$53 \leq \text{Visit 3-Baseline} \leq 59$
Visit 4	84	± 3	$81 \leq \text{Visit 4-Baseline} \leq 87$
Visit 5	112	± 4	$108 \leq \text{Visit 5-Baseline} \leq 116$
Visit 6	168	± 7	$161 \leq \text{Visit 6-Baseline} \leq 175$
Visit 7	252	± 7	$245 \leq \text{Visit 7-Baseline} \leq 259$
Visit 8	336	± 7	$329 \leq \text{Visit 8-Baseline} \leq 343$

Table 3 Analysis visit definition – 0-12 Vaccination schema

Analysis visit	Visit day Interval (days)	Visit window (days)	Analysis visit permitted window (days)
Visit 1(Baseline)	0		
Visit 2	7	± 2	$5 \leq \text{Visit 2-Baseline} \leq 9$
Visit 3	84	± 3	$81 \leq \text{Visit 3-Baseline} \leq 87$
Visit 4	112	± 3	$109 \leq \text{Visit 4-Baseline} \leq 115$
Visit 5	140	± 4	$136 \leq \text{Visit 5-Baseline} \leq 144$
Visit 6	168	± 7	$161 \leq \text{Visit 6-Baseline} \leq 175$
Visit 7	252	± 7	$245 \leq \text{Visit 7-Baseline} \leq 259$
Visit 8	336	± 7	$329 \leq \text{Visit 8-Baseline} \leq 343$

8.4 Derived or transformed variables

The baseline is defined as last non-missing value on or prior to the start date of IP administration.

Table 4 Derived Variables

Variables	Method
Change from baseline	Post-baseline value – Baseline value
Age group	Age < 66y old, Age \geq 66y old
Total dose (mg)	Sum of investigational product doses at each time point
GMT	$10^{\text{Mean of log}_{10} \text{ value}}$

CONFIDENTIAL

Variables	Method
Change from baseline (GMT)	$10^{(\text{Mean of } (\log_{10} \text{post} - \text{baseline value} - \log_{10} \text{baseline value}))}$
GMR	$10^{(\log_{10} \text{GMT1} - \log_{10} \text{GMT2})}$
AE Duration (days)	AE end date – AE start date+1 if AE end date is ongoing, replaced with last visit date and add symbol (\geq) (ex. ≥ 15)
Occurrence Duration (days)	AE start date – Investigational product start date

9. Subject Information

Subject information will be analyzed on ITT.

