6.2 Packaging and Labeling

Study product will be labelled as shown in Table 5.2-1.

Investigational products are labeled with whether the vial contains the GLS-5310 DNA vaccine or SSC placebo, as shown in Table 5.2-1.

Table 6.2-1. Study drug product labels (for Phase I)

Biologic Product/ Placebo	Sample Label
GLS-5310	GLS-5310 [6 mg/ml] 0.3 mL/Vial Single Use Vial Lot: GLS-5310xxxx Date of Manufacture: DD MMM YYYY Final Retest Date DD MMM YYYY Store at 2 - 8°C CAUTION New Drug – Limited by Federal Law to Investigational Use GeneOne Life Science, Inc.
SSC	SSC 0.3 mL/Vial Single Use Vial Lot: xxxx.xxxxx Date of Manufacture: DD MMM YYYY Final Retest Date DD MMM YYYY Store at 2 - 8°C CAUTION New Drug – Limited by Federal Law to Investigational Use GeneOne Life Science, Inc. Rev 000

For the Phase IIa portion of the study, the unblinded site pharmacist will dispense filled syringes to blinded study personnel that are labelled with only the subject ID# to maintain treatment blind.

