7.1.11 Unscheduled visits

Study procedures to be completed include:

- Review and record concomitant medications
- Perform targeted physical exam (relevant to participant system-specific complaints)
- Perform and record vital signs
- Review and record adverse events

7.2 Procedures by Visit (GLS-5310 revaccination group, see clinical trial schedule S4)**7.2.1 Visit 1: Vaccination**

- Review and record prior and concomitant medications
- Perform and record physical examination and vital signs
- Collect blood for hematology and chemistry safety labs (baseline values)
- Collect blood for immunology testing (serum and PBMCs baseline values)
- Collect urine for pregnancy testing (women of childbearing potential)
- Administer study drug (GLS-5310)
- Perform VAS score and record
- Distribution of subject diary after vaccination
- Check whether or not immediate adverse events (anaphylaxis-related) occur within 30 minutes after vaccination of the investigational drug (in case of the elderly over 75 years of age in Phase 2a, immediate adverse events are observed until at least 2 hours after vaccination of the investigational drug)

7.2.2 Visit 2: Safety follow-up.

Study procedures to be completed include:

- Review and record concomitant medications
- Perform targeted physical exam (relevant to participant system-specific complaints)
- Perform and record vital signs
- Review and record adverse events
- Review and record injection site reactions
- Review of subject diary
- Collect blood for hematology and chemistry

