4.1 Interim Analysis

Interim analyses were performed in stages.

- **Stage 1:** An assessment of AE's was performed after study Visit 1 for Group 1a.
- **Stage 2:** When all Phase I subjects (Groups 1a, 1b and 1c) had completed Visit 4, an interim analysis was performed to evaluate safety and antibody response.
In order for the study to move into Phase IIa study, the seroconversion rate for the binding antibody responses must be >70%. In addition, the incidence of Serious Adverse Events (Grade 3 or higher) related to the investigational product should be no more than 1 case.
- **Stage 3:** An interim analysis of Phase IIa study was performed after all patients complete their Visit 4. The purpose of this interim analysis was to provide options to placebo vaccinated subjects and to assess the safety of the vaccine after the second dose. For the interim analysis of Phase IIa, database locking was implemented before unblinding.

The study is unblinded at the post-vaccination visit (study Visit 4) at which time subjects are informed of their treatment assignment. Subjects who were assigned to the placebo group are offered to be vaccinated with GLS-5310. Subjects assigned to the placebo group who choose to be vaccinated with GLS-5310 are followed for a year from 1st GLS-5310 vaccination; subjects assigned to the placebo group but who decline vaccination with GLS-

CONFIDENTIAL

5310 are followed for a year from study entry as per the original study protocol.

5. Determination of Sample Size

This is an exploratory and descriptive Phase I/Ila clinical trial to evaluate the safety and immunogenicity of GLS-5310 for the purpose of preventing COVID-19, and dose not test statistical hypotheses, so the sample size is set within the limit of satisfying the research purpose. In the Phase I clinical trial, 45 subjects who meet the inclusion and exclusion criteria are registered to secure 15 subjects based on the allocation of each vaccination group. In the Phase Ila clinical trial, it is planned to secure 120 subjects based on randomization.

Randomization is performed 1:1 in 1b and 1c groups of Phase I clinical trial according to the planned random number, and 1:2 in placebo and vaccination groups in Phase Ila clinical trial to determine the difference between placebo and vaccination groups.

6. Analysis Sets

Safety and tolerability analyses will be performed on Safety Set.

✓ **Intention to treat (ITT)**

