Intention to treat (ITT) will include all participants who sign informed consent.

✓ **Modified Intention to treat (mITT)**

Modified intention to treat (mITT) will include all participants who sign informed consent and who have received at least one administration of investigational product. The mITT will be the primary analysis population for baseline and demographic assessments and efficacy outcomes. All subjects will be summarized based on the treatment group to which they were assigned. Since not all subjects will have evaluable immune response data, analysis of immune responses will be performed only for available samples.

✓ **Safety Set (SS)**

Safety Set (SS) will include all mITT participants. The SS will be the primary population for summary and analysis of safety assessments. All subjects will be summarized based on the treatments that actually received.

✓ **Per-Protocol Set (PPS)**

Per-Protocol Set (PPS) will include all mITT participants who complete the trial by receiving all

CONFIDENTIAL

vaccinations and have no significant protocol violations. This set will be used as a sensitivity analysis to summarize the primary and secondary response outcomes. For secondary and exploratory assessments of antibody and T cell immune responses, denominators will include only those participants who are SARS-CoV-2 seronegative at baseline. Unevaluable samples will not be considered as part of the denominator at relevant time points.

Protocol violations that can be excluded from the analysis group include the following and are defined according to the analysis population's definition of 'SOP 0406'.

- Participants who have never been vaccinated with all vaccinations
- Positive for SARS-CoV-2 serum test at Baseline
- Inclusion/Exclusion criteria violation
- Contraindicated drug administration
- Randomization errors
- Vaccination errors
- No blood draw for immunogenicity assessment

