8.2 Handling of Missing Data

If there are missing dates and are used in calculations, they will be imputed as the following:

Table 1 Handling of missing or partial date

Types of Dates	Missing	Imputation	Examples
Prior/ Concomitant medication start date	YYYY-MM-DD	Year of the date of informed consent-01(January)-01	Date of informed consent: 2018-12-05 Collected date: UK-UK-UK Imputed date: 2018-01-01

CONFIDENTIAL

Types of Dates	Missing	Imputation	Examples
	MM-DD	01(January)-01	Collected date: 2018-UK-UK Imputed date: 2018-01-01
	DD	01	Collected date: 2018-12-UK Imputed date: 2018-12-01
Prior/ Concomitant medication end date	YYYY-MM-DD	Final visit date	Final visit date: 2018-12-25 Collected date: UK-UK-UK Imputed date: 2018-12-25
	MM-DD	12-31	Collected date: 2018-UK-UK Imputed date: 2018-12-31
	DD	Last day of the month	Collected date: 2018-12-UK Imputed date: 2018-12-31
AE start date	YYYY-MM-DD	First IP administration date	Date of first IP administration: 2018-12-05 Collected date: UK-UK-UK Imputed date: 2018-12-05
	MM-DD	1. The year of the IP administration date = The year of the AE start date: The month and day of the IP administration date 2. The year of the IP administration date ≠ The year of the AE start date: 01-01	1. Date of IP administration: 2018-12-05 Collected date: 2018-UK-UK Imputed date: 2018-12-05 2. Date of IP administration: 2018-12-05 Collected date: 2019-UK-UK Imputed date: 2019-01-01
	DD	1. The year and the month of the IP administration date = The year and the month of the AE start date: The day of the IP administration date 2. The year and the month of the IP administration date ≠ The year and the month of the AE start date: 01	1. Date of IP administration: 2018-12-05 Collected date: 2018-12-UK Imputed date: 2018-12-05 2. Date of IP administration: 2018-12-05 Collected date: 2019-05-UK Imputed date: 2019-05-01
AE end date	YYYY-MM-DD	1. If the subject is dead: Death date 2. If the subject is not dead and has date of the last observation/date of early termination: Last observation/date of early termination	1. Death date: 2018-12-30 Collected date: UK-UK-UK Imputed date: 2018-12-30 2. Last observation/early termination date: 2018-12-30 Collected date: UK-UK-UK Imputed date: 2018-12-30

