10.1 Extent of Exposure

Total number of vaccinations (times) and total dose (mg) will be summarized with number of subjects, mean, standard deviation, median, minimum, and maximum by vaccination group.

* Total dose is defined as sum of study drug doses at each time point.

- Total Dose in Placebo / GLS-5310 0.6 mg / GLS-5310 1.2 mg (8W) / GLS-5310 1.2 mg (Re-vac.) = Dose at Baseline + Dose at Week 8
- Total dose in GLS-5310 1.2 mg (12W) = Dose at Baseline + Dose at Week 12

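### The SAP's baseline, adverse-event date and visit-window rules are not adapted to the re-vaccination group; read literally, they start from the placebo dose

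*SAP*

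**What the plan says.** **The rules as written.** SAP 8.4 gives a single baseline for everyone: "The baseline is defined as last non-missing value on or prior to the start date of IP administration". The same section computes the time to onset of an AE as "AE start date – Investigational product start date". SAP 8.2, Table 1, imputes a fully missing AE start date to the "First IP administration date" and resolves partial dates against the IP administration date. SAP 8.3 defines analysis visits as days from baseline, in one table for the 0-8 schema (Table 2) and one for the 0-12 schema (Table 3). SAP Table 6 sets the neutralizing cut-off at 4 times, and the ELISPOT cut-off at 2 times, a Day 0 response that is not defined further. SAP 10.2 ties treatment emergence to the initial IP vaccination.

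**The group they must serve.** Placebo participants who accept GLS-5310 after unblinding form a separate reporting group and "are followed for a year from 1st GLS-5310 vaccination" (SAP 4.1). Protocol Table S4 gives them a new schedule starting again at Visit 1. Protocol 7.2.1 has new samples drawn there: "Collect blood for immunology testing (serum and PBMCs baseline values". SAP 10.1 defines their exposure as "GLS-5310 1.2 mg (Re-vac.) = Dose at Baseline + Dose at Week 8".

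**The concern.** Placebo counts as IP in these documents. Protocol 6.2 says "Investigational products are labeled with whether the vial contains the GLS-5310 DNA vaccine or SSC placebo", and the mITT takes consented participants "who have received at least one administration of investigational product" (SAP 6), which would exclude the placebo arm if placebo were not IP. For a re-vaccinated participant, the start of IP is therefore literally the placebo dose. No passage in SAP 8.2 to 8.4 or Table 6 replaces that date with the first GLS-5310 dose.

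At stake is the usability of this group's own results: which visit a sample belongs to, what a fold-rise is measured against, and whether an AE is placed before or after the first active dose. The last matters because Protocol 11.1 assigns safety by treatment actually received and Protocol 11.8 reports these participants as a separate safety group.

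**Working it through.** **Inputs.**
- Crossover: Week 12, day 84, with a Visit 4 window of ±3 days (Protocol 11.1, Table S2).
- Re-vaccination visits: Weeks 0, 1, 8, 12, 20, 24, 36 and 48 (Table S4).
- Analysis windows: SAP Table 2.
- Group size: at most 40, the placebo arm (Table S1). Uptake is not stated.

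**Reproducing the plan's figures.** Each Table 2 window for Visits 2 to 8 equals week × 7 ± the Table S2 window; for example, Visit 4 is 12 × 7 ± 3 = 81 to 87. Total follow-up is 12 + 48 = 60 weeks, as the protocol synopsis states, or 420 days. The last Table 2 window ends at day 343.

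**Placing the Table S4 visits in Table 2.** Day from placebo = Table S4 day + 84.

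| S4 visit | Day from first GLS-5310 dose | Table 2 label | Day from placebo dose | Table 2 label |
|---|---|---|---|---|
| 1 | 0 | Visit 1 | 84 | Visit 4 |
| 2 | 7 | Visit 2 | 91 | none |
| 3 | 56 | Visit 3 | 140 | none |
| 4 | 84 | Visit 4 | 168 | Visit 6 |
| 5 | 140 | none | 224 | none |
| 6 | 168 | Visit 6 | 252 | Visit 7 |
| 7 | 252 | Visit 7 | 336 | Visit 8 |
| 8 | 336 | Visit 8 | 420 | none |

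From the placebo dose, 0 of 8 visits keep their own label; four take another visit's label and four fall in no window. The nominal-day result is the same with crossover at day 81 or 87. From the first GLS-5310 dose, 7 of 8 are placed correctly. Visit 5 (140 ± 4 = 136 to 144) lies between the Table 2 windows for Visit 5 (108 to 116) and Visit 6 (161 to 175).

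**Table 3 is no substitute.** Its Visit 5 window is 136 to 144, but its Visits 3 and 4 are at days 84 and 112, against 56 and 84 in Table S4.

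**AE start dates, taking the placebo dose as the IP date in Table 1.** An AE that began after GLS-5310 would be dated before it in these cases:
- Date fully missing: set to the placebo dose, about 84 days (81 to 87) before the first GLS-5310 dose.
- Month and day missing, same year as the placebo dose: also set to the placebo dose.
- Only the day missing, in the crossover month: set to the 1st of that month, because the month differs from the placebo month. This precedes the GLS-5310 dose unless that dose was given on the 1st.

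The SAP 8.4 time to onset would likewise be about 84 days too long.

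**Immunogenicity.** The neutralizing and ELISPOT cut-offs and the GMT fold increases (SAP 11.1, 11.2) would be taken against the pre-placebo sample. The binding responder rule is an absolute titer above 50 and uses no baseline. The size of any change in fold-rise cannot be computed, since no titers are given.

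**Cross-check on intent.** Under the placebo anchor, SAP 10.1 would give this group 0 + 0 = 0 mg. Under the GLS-5310 anchor it gives 1.2 + 1.2 = 2.4 mg, which fits the group's label.

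**The case against.** The strongest reply is that the intended anchor is plain. The baseline sentence does not say first, and Day 0 and the IP start date in SAP 8.4 are not tied to a period. SAP 10.1 makes sense only if baseline is the first GLS-5310 dose. Protocol 7.2.1 collects new baseline samples, Table S4 restarts at Visit 1, and follow-up runs from the first GLS-5310 dose. A programmer who reads all of this would probably not produce the right-hand columns of the table. The TLF shells listed in the SAP contents are not in the public text and may set the visit labels.

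Much of this stands. A reader might infer that the SAP fixes every anchor at the placebo dose and that this group's results are computed from the wrong day. The documents do not support that.

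Nor do they support saying that an infection before crossover would generally count as vaccine response because of the anchor. Antibody from such an infection could pass the binding threshold of 50 under either anchor; only the cut-offs and changes relative to Day 0 depend on it. It would also be too broad to say that all AEs with incomplete dates move back to the placebo dose. For example, an AE with only the day missing, in a month after crossover, is still dated after the first GLS-5310 dose.

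The reply does not dispose of two things. Table 1 does say first, so the fully missing case has a stated rule that gives the wrong period. And Table S4 Visit 5 has no window under any anchor. SAP 10.1 defines total dose only; it does not amend baseline, windows or imputation.

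**Conclusion.** The point holds as a gap in the data-handling rules: they were not carried over to a group that the SAP reports separately. Two competent programmers could derive different datasets from this text, and one of them, reading literally, would mislabel or drop every Table S4 visit. The Visit 5 mismatch is the firmest part, because it needs no assumption about the anchor.

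The reach is limited. At most 40 participants are involved, in a group neither pooled nor compared with the randomized vaccine arm. The randomized comparison to Visit 4 is unaffected. The number of AEs with incomplete dates is unknown.

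The conclusion assumes that placebo is IP, which Protocol 6.2 and the mITT definition support although Protocol Table 6.1-1 lists the two in separate columns, and that crossover is at about day 84. A later crossover would change which wrong label a visit takes. It could not restore the right one, because the shift far exceeds the widest window of ±7 days. The SAP should be amended; the remedy is cheap.

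**What to change.** In SAP 8.2 to 8.4, 10.2 and Table 6, state for the re-vaccination group that:

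- baseline is the last non-missing value on or before the first GLS-5310 dose;
- Day 0, the IP start date, treatment emergence and the anchor for imputing AE dates all refer to that dose;
- a missing or partial start date of an AE first reported after crossover is imputed no earlier than that dose.

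In SAP 8.3, add an analysis-visit window table that follows Table S4, with Visit 5 at Week 20 (days 136 to 144). Re-anchoring alone would leave that visit unplaced.

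The cost is a few sentences, one short table and a period flag in the programs. No data collection changes.

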9.1 Subject Disposition

The following subjects or reason will be summarized using number of subjects and percentages by vaccination group and overall. The screened, screened fail and study completion status of subjects will also be summarized by study sites using number of subjects and percentages by vaccination group and overall.

- Screening/Screening fail
- Reason for Screening fail
- Follow-up continued (V4)/Discontinued (V4)
- Study Completed/Discontinued
- Reason for discontinuation

9.2 Protocol Deviation

Subjects who are excluded from analysis sets (ITT, mITT, SS, and PPS) and the details will be presented in a listing.

9.3 Analysis Sets

The number of subjects included in each population set (ITT, mITT, SS, and PPS) and the percentages will be summarized by vaccination group. The reasons of exclusion from each set will also be summarized using number of subjects and percentages by vaccination group.

9.4 Demographics and Baseline Characteristics Analyses

Demographics and Baseline Characteristics will be summarized on mITT.

CONFIDENTIAL

9.4.1 Demographics and Baseline Characteristics

For the following variables, the continuous variables will be summarized with number of subjects, mean, standard deviation, median, minimum, and maximum by vaccination group. The categorical variables will be summarized using number of subjects and percentages by vaccination group.

- Age(years), Age group (<66y old, ≥66y old, for Phase IIa), Sex, Fertility status, Alcohol, Smoking
- Alcohol consumption (Units/week), Height (cm), Weight (kg), BMI (kg/m²)
- 12-Lead Electrocardiogram (ECG) : Heart rate (bpm), PR (msec), QRS (msec), QT (msec), QTcF (msec), ECG result, PCR/Antibody test results for SARS-CoV-2 infection at baseline)

9.4.2 Medical History and Comorbidities

Previous medical history will be defined as those that are checked “No” for the question “Ongoing” under [Medical History] page of the CRF, and comorbidities will be defined as those that are checked “Yes” for the same question.

Medical history and comorbidities will be coded with medical dictionary for regulatory activities (MedDRA) version 25.0 and will be summarized with system organ class (SOC) and preferred term (PT) by vaccination group using number of subjects and percentages.

9.4.3 Prior and Concomitant Medications

Prior medication will be defined as any medication that the subjects took in past 24 weeks and stopped prior to the first vaccination of investigational product. Only, prior medications associated with exclusion criteria will be recorded based on the time point of taking the medications.

Concomitant medication will be defined as any medication that the subjects took after the first vaccination of investigational product, including any prior medications that were ongoing at the time of first vaccination.

Prior medication classification

- Medication start date < Date of first vaccination of investigational product (Date of V1) or
- Medication end date ≤ Date of first vaccination of investigational product (Date of V1)

Concomitant Medications classification

- Medication start date ≥ Date of first vaccination of investigational product (Date of V1) or
- Medication end date ≥ Date of first vaccination of investigational product (Date of V1) or
- Ongoing

Prior and concomitant medications will be coded using world health organization anatomical therapeutic

CONFIDENTIAL

chemical index (WHO ATC index) 2022 and will be summarized with level1 (anatomical main group) and level 5 (chemical substance) by vaccination group using number of subjects and percentages. If level 5 (chemical substance) does not exist or 'Combinations' and/or 'Various', higher level will be used instead.

10. Safety and Tolerability Analyses

Safety and tolerability analyses will be performed on SS.

